### **OLE Phase:**

For reporting the OLE analyses, no data cut-off will be applied to the datasets. Only data related to the OLE Phase will be reported:

- Demographics and baseline characteristics for patients who received at least one dose of study drug within the OLE Phase
- Baseline safety and efficacy data ([section 9.3](#))
- Safety and efficacy reported during the OLE Phase
- AEs and concomitant medications started on or after the 1st dose of OLE study drug intake

## 10 Analysis Sets

**For the Double-Blind Treatment Phase:** Safety analyses will be conducted for the safety population. The mITT population will be used for the primary efficacy analysis. The PK population will be used for PK analyses. Patients will be analyzed according to their randomized treatment for efficacy assessments and according to the actual treatment received for safety assessments.

**For the OLE Phase:** The open-label safety population will be used.

## 10.1 Modified Intent-to-Treat Population

The mITT population will include all randomized patients who received at least one dose of study drug and have one baseline and at least one post-baseline assessment during the Double-Blind Treatment Phase. This population will be used to summarize the primary, secondary, and other efficacy data. Patients will be analyzed according to their randomized treatment.

## 10.2 Double-Blind Safety Population

The Double-Blind safety population will include all patients who are enrolled and take at least one dose of double-blind study drug. Patients will be analyzed according to their treatment received. In the case of mis-dosing, patients will be counted at the highest dose they received in the Double-Blind Treatment Phase.

## 10.3 Open-Label Safety Population

The Open-Label safety population will include all patients who are enrolled in the OLE Phase and take at least one dose of open-label study drug.

## 10.4 Pharmacokinetic Population

The PK population will include all patients who received at least one dose of study drug and have calculable concentrations of pitolisant available for analysis.

# 11 Statistical Methods

All analyses will use SAS version 9.4 or higher.

Categorical variables will be summarized using counts and percentages based on the specified population total. Percentages will be rounded to one decimal place, except 100% will be displayed without any decimal places and percentages will not be displayed for zero counts.

Continuous data will be summarized using non-missing observations (n, mean, SD, median, minimum, and maximum). The minimum and maximum values will be displayed to the same level of precision as the raw value. Mean, and median will be rounded to 1 decimal place greater than precision of the original value. The SD will be rounded to 2 decimal places greater than precision of the original value. Confidence intervals (CI), least squares (LS) means, and standard error (SE) will be provided as appropriate. CIs, LS means will be presented with a precision similar to mean and SEs will be presented with a precision similar to SD.

This is an exploratory study. Except for the analysis of the SART endpoint (using Kruskal Wallis test and for which the p-value will be reported), no formal statistical hypothesis testing (including the generation of p-values) is planned for other study endpoints. For these endpoints, the p-values will be included in supporting statistical appendix.

All listings will be displayed by treatment arm (where applicable), patient identifier and date of assessment. Age, sex, and race will be presented.

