### **METHODOLOGY**:

### **Double-Blind, Placebo-Controlled Treatment Phase:**

After completion of the Screening Period, eligible patients who agree to participate will be randomized in a 1:1:1 ratio to one of three treatment groups: lower dose pitolisant (17.8 mg), higher dose pitolisant (35.6 mg), or placebo. Study drug doses will be titrated during a 3-week period (Day 1 to 21):

- Pitolisant lower dose 17.8 mg treatment group: Week 1 (Day 1-7), 4.45 mg; Week 2 (Day 8-14), 8.9 mg; Week 3 (Day 15-21), 17.8 mg
- Pitolisant higher dose 35.6 mg treatment group: Week 1 (Day 1-7), 8.9 mg; Week 2 (Day 8-14), 17.8 mg; Week 3 (Day 15-21), 35.6 mg
- Patients randomized to placebo will receive matching doses of placebo tablets over the 3-week Titration Period and during the Stable Dose Period.

Adjustments to study drug dosing outside of the protocol-specified titration schedule are not allowed during the 11-week Double-Blind Treatment Phase.

Efficacy assessments will be performed at the Baseline Visit (Day -1), Visit 4 (Day 49), and Visit 5 (Day 77), with the exception of the optional Maintenance of Wakefulness Test (MWT), Cogstate Computerized Cognitive Battery Tests and Sustained Attention to Response Task (SART), which are

only to be performed at the Baseline and End of Treatment (EOT) study visits. At the end of the Double-Blind Treatment Phase (Day 77/Visit 5), patients who do not enter the optional OLE Phase will have two safety follow-up telephone contacts (TCs), one 15 ( $\pm$ 3) days and another 30 (+3) days after the final dose of blinded treatment.

Safety assessments will include electrocardiograms (ECGs; in triplicate) at Screening, Baseline, Day 22 (Visit 3), Day 49 (Visit 4), and Day 77 (Visit 5). In addition to ECG testing, Holter monitoring will be performed during Screening and at Visit 3 (Day 22). On those days when a Holter monitor is placed on the patient, the ECG data will be taken from the Holter monitor recording. Any clinically significant finding from Holter monitoring requires additional evaluation (including an unscheduled ECG). Adverse event (AE) and concomitant medication monitoring and Columbia-Suicide Severity Rating Scale (C-SSRS) assessment will be conducted at all visits whether on-site or by TC. Patients will receive TCs from the site on Days 8, 15, and 28.

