### 9.1.2. Multiple Comparisons

The DSS will be the primary endpoint measure. All statistical analyses will be purely descriptive.

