### 9.4.2.1.2. Secondary Efficacy Analysis

Analysis of the secondary efficacy endpoints will utilize parallel methodology to that used for the primary efficacy analysis, adjusted as appropriate for distributions and collection time points. Full details will be provided in the SAP.

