## 6 Introduction

This SAP should be read in conjunction with the study protocol Amendment 5 dated 18 July 2023 and electronic case report form (eCRF) v4.0 dated 09May2023. Any changes to the protocol or eCRF may necessitate updates to the SAP.

The SAP Version 1 was approved on 28 April 2021. This SAP Amendment 1 (Version 2.0) will include changes to the protocol through protocol Amendment 5. Final approval of the SAP by Harmony Biosciences, LLC and ICON will occur prior to the database entry lock and unblinding of the database for the analyses of the Double-Blind Treatment Phase of the study.

If the statistical analyses described in the final SAP and final protocol differ, the statistical analyses in the SAP will be used for the analyses presented in the clinical study report (CSR). Substantive changes from the analyses specified in the protocol will be described in the SAP and in the CSR.

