### 6.1 Changes from Protocol

The Intent-to-Treat Population referenced in protocol Amendment 4 is referred to as the modified Intent-to-Treat Population (mITT) in the SAP; the definition remains same.

For the Open-Label Extension (OLE) Phase reporting, all patients will be analyzed as a single group, which will be labelled "Total". All patients will be titrated during a 3-week Titration Period to a dose of 35.6 mg pitolisant (or a maximum dose up to 35.6 mg based on Investigator assessment of tolerability). Additional changes from protocol Amendment 4 include:

- Removed sample size and statistical power calculation
- Removed Z-score (aggregation of Daytime Sleepiness Scale [DSS] and Mean Sleep Latency [MSL]) endpoint
- Removed Maintenance of Wakefulness Test (MWT) population
- Replaced Analysis of Covariance (ANCOVA) with Mixed Model Repeated Measures (MMRM) for primary endpoint analysis method
- Removed analysis of site effect in statistical models for study endpoint analysis
- Removed multiple imputation (MI) and sensitivity analyses

---

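### SART alone has p-values reported as results in a descriptive trial, and alone in SAP Table 7 has no adjusted difference from placebo

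*SAP*

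**What the plan says.** Protocol 9.1.2 states: "All statistical analyses will be purely descriptive". SAP section 11 calls the study exploratory but makes an exception: "Except for the analysis of the SART endpoint (using Kruskal Wallis test and for which the p-value will be reported". For everything else, "no formal statistical hypothesis testing (including the generation of p-values) is planned for other study endpoints". The next sentence reads: "For these endpoints, the p-values will be included in supporting statistical appendix".

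SAP 11.4.3.1.10 applies the exception to the SART go, no-go and total scores. It assumes that their changes from baseline are not normally distributed. It plans descriptive statistics, and reported p-values for lower dose, higher dose and pooled pitolisant against placebo. It mentions no estimated difference or confidence interval. Table 7 gives the method as Kruskal-Wallis. The example code in Appendix 4 is a one-way rank procedure on change from baseline, with treatment as the only factor and the `dscf` option for pairwise comparisons.

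The other Table 7 endpoints use MMRM or ANCOVA with baseline value and the wake-promoting stratum as terms, and report LS-mean differences from placebo. Protocol 9.4.2.1.2 lets secondary methods follow the primary one, "adjusted as appropriate for distributions and collection time points".

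**The concern.** There are two problems.

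The first is emphasis. In the body of the report, the only p-values would belong to one secondary attention task, while those for the primary DSS endpoint would sit in an appendix. Neither document gives a reason. Assumed non-normality can explain a rank test, but not why its p-value alone is a reported result. SAP section 11 also contradicts itself by ruling out p-values for the other endpoints and then placing them.

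The second is a missing estimate. An exploratory study of about 10 patients per arm is read mainly through differences and their intervals. For SART the reader gets arm summaries and p-values, but no planned contrast with an interval and no adjustment for the baseline score or the randomisation stratum, both of which are available. SAP Table 3 lists SART and Cogstate Identification as attention measures under one objective. Identification is to have an adjusted difference and an effect size, so the two could not be compared on the same footing.

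**Working it through.** The plan states no figure on this point, so the check is mainly textual, with one calculation on the printed test.

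**1. Table 7, row by row.** Six rows use MMRM (DSS, ESS, FSS, MDHI, CGI-S, PGI-S), four use ANCOVA (three Cogstate tests, MSL) and three use Kruskal-Wallis (SART go, no-go, total): 6 + 4 + 3 = 13. Against the endpoint sections and Appendix 4, a difference adjusted for baseline and stratum is planned in 10 of 10 non-SART rows and 0 of 3 SART rows.

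**2. Does the visit schedule explain it?** No. The protocol synopsis says that the optional MWT, the Cogstate tests and SART are "only to be performed at the Baseline and End of Treatment (EOT) study visits". That explains why SART has no MMRM. But MSL and the Cogstate tests share the schedule and still get an ANCOVA.

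**3. Does the code deliver what the text promises?** The text promises 3 scores × 3 comparisons = 9 p-values. With three arms, DSCF gives three pairs per score: lower–placebo, higher–placebo and lower–higher. Only two of these are wanted, so the code yields 3 × 2 = 6 of the 9. Pooled versus placebo is not produced.

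**4. How strict is a DSCF pair?** Assume 10 complete patients per arm (30/3), no ties, and the usual large-sample reference for DSCF.
- The 5% critical value of the studentized range for three groups is 3.314. On the z scale this is 3.314/√2 = 2.344.
- The SD of the rank sum for 10 versus 10 is √(10 × 10 × 21/12) = 13.23.
- Rejection needs a deviation of at least 2.344 × 13.23 = 31.0. Unrounded this is 31.004, so the smallest attainable deviation is 32.
- Under no effect, 2,714 of the 184,756 equally likely allocations reach that: 1.47%.

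An unadjusted two-group rank test would reject close to 5% of the time. DSCF pairs are stricter because the method controls error over all three pairs. The SAP does not say which is intended.

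**5. What could adjustment gain?** For equal variances σ² and baseline/Week 11 correlation r, raw change has variance 2σ²(1 − r) and baseline-adjusted change has σ²(1 − r²). The ratio of adjusted to raw is (1 + r)/2: 0.65, 0.75 and 0.85 at r = 0.3, 0.5 and 0.7. The documents give no r for SART.

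**6. Illustration only.** All inputs are assumed: normal data, 10 per arm, a 1 SD effect in both active arms, 4 of 10 per arm on wake-promoting agents, and a 0.5 SD stratum shift at both visits. The comparison is higher dose versus placebo, two-sided 0.05.

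| r | DSCF pair | unadjusted rank test | ANCOVA |
|---|---|---|---|
| 0.3 | 0.23 | 0.42 | 0.60 |
| 0.5 | 0.33 | 0.55 | 0.68 |
| 0.7 | 0.55 | 0.76 | 0.84 |

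With skewed (lognormal) data, an unadjusted rank test overtakes the ANCOVA at r = 0.8 (0.62 against 0.59) and r = 0.9 (0.75 against 0.69), for effects of 0.6 and 0.5 SD. The ANCOVA 95% CI covered 94.7–95.6% in the normal and skewed cells, with mean half-width from 0.89 SD (r = 0.3) to 0.41 SD (r = 0.9).

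**The case against.** **The SAP prevails.** Both documents say that the SAP governs where they differ, so the SART exception is authorised. That stands. A reader might infer an undisclosed departure because SAP section 6 promises that "Substantive changes from the analyses specified in the protocol will be described in the SAP and in the CSR" and section 6.1 omits SART while listing items such as "Replaced Analysis of Covariance (ANCOVA) with Mixed Model Repeated Measures (MMRM) for primary endpoint analysis method". The documents do not support that. SAP section 11 states the exception openly, and the 6.1 list is framed against Amendment 4, whereas the descriptive-only wording came with Amendment 5. What remains is that the exception is unexplained.

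**The rank method is legitimate.** It is. The protocol allows methods suited to the distribution and the SAP assumes non-normality, so the Kruskal-Wallis test is neither invalid nor forbidden. For the same reason, making a normal-theory ANCOVA the lead SART result would be a trade-off, not a correction.

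**The size of the effect can be recovered.** A reader might infer that SART results could not be quantified at all. That goes too far. SAP sections 11, 11.4.3 and 11.4.3.1.10 plan n, mean and SD of change by arm and for the active arms combined. An unadjusted difference and its standard error, √(s₁²/n₁ + s₂²/n₂), follow. What is missing is a planned, adjusted contrast with an interval.

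**The ANCOVA is not clearly more powerful.** This stands too. The simulated gain depends on wholly assumed inputs and reverses in some skewed cells, so it should not carry the argument.

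**Appendix 4 gives only examples.** True, but it is the only place that indicates a pairwise method, so the ambiguity is real.

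**A rank-based shift estimate would do.** A Hodges-Lehmann shift with its interval would suit the rank test and partly fill the gap. In its usual form it adjusts for neither baseline nor stratum.

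**Conclusion.** The point holds as one of consistency, emphasis and a missing estimate. SART is the only endpoint whose p-values are reported as results in a study declared descriptive, and SAP section 11 contradicts itself on the p-values of the others. All three SART rows lack the adjusted difference that the ten other Table 7 rows have. The printed code cannot supply the pooled comparison, and its pairwise tests run at about 1.5% per pair under no effect, given 10 complete patients per arm and no ties.

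The validity of the trial and of the primary analysis is not touched, and no claim of a general power gain is made. The comparison with Cogstate Identification rests on the SAP text; fuller details are in a separate Cogstate SAP that is not among the documents. Confidence in the textual findings is high. Their practical weight is low, so this is an optional improvement.

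**What to change.** 1. For the go, no-go and total scores, add beside the rank test the difference from placebo in change from baseline (higher, lower and pooled) with a 95% CI, adjusted for baseline and wake-promoting stratum. The Appendix 4 ANCOVA does this once `trtpn` is named in its `estimate` line, which as printed names no effect.
2. Keep the rank test. State whether its pairwise p-values are DSCF-adjusted or come from separate two-group tests, and run pooled versus placebo as its own two-group test.
3. Put all p-values, SART included, in the statistical appendix, labelled nominal. Reword SAP section 11 and 11.4.3.1.10 to match.

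The cost is a few lines of SAP text and one existing model call per score. Baseline SART and the stratum are already collected. The change is best made before the double-blind data are unblinded.

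The downside is that there would be no headline SART p-value, and the two methods may sometimes disagree. In the simulations with an effect, the ANCOVA and an unadjusted rank test fell on opposite sides of 0.05 in 8–30% of runs (3–6% with none). The text should therefore say that the estimate and interval are descriptive, and that neither result is a test of efficacy.

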## 11.1 Patient Disposition

### 11.1.1 Disposition

For the Double-Blind Treatment Phase, the number and percentage of patients screened, enrolled, completing the Double-Blind Treatment Phase, discontinuing from the Double-Blind Treatment Phase, and enrolled in OLE will be summarized, together with a breakdown of the corresponding reasons for withdrawal from study drug and from the study. Also, the number and percentage of patients included in each analysis set will be summarized.

---

The number of patients who screen failed and the reason for screen failure will be tabulated. A supportive data listing will be provided for the screen failure patients and will include the reason for screen failure and the list of inclusion/exclusion criteria failed.

For the OLE Phase, the number and percentage of patients enrolled in the OLE Phase, completing the OLE Phase, discontinuing treatment and/or from the OLE Phase and the reasons for discontinuation from the treatment and/or the OLE Phase will be summarized.

Patient disposition data will be presented in a data listing for Double-Blind safety and open-label safety populations.

### **11.1.2 Important Protocol Deviations**

The number and percentage of patients with important protocol deviations (PD) by category will be summarized by treatment arm, active arms pooled, and overall for the Double-Blind Treatment Phase and total for the OLE Phase.

Important PDs will be listed. All COVID-19 related PDs will be listed separately.

### **11.1.3 Inclusion and Exclusion Criteria**

Failed inclusion and exclusion criteria for the randomized patients will be presented in a data listing.

## **11.2 Demographic and Baseline Characteristics**

### **11.2.1 Demographics**

Baseline data will be summarized for continuous and categorical variables as applicable.

The following demographic and baseline characteristics will be summarized:

- Sex (female, male)
- Race (White, Black or African American, Asian, American Indian or Alaska Native, Native Hawaiian or Other Pacific Islander)
- Ethnicity (Hispanic or Latino, not Hispanic or Latino, Not Reported, Unknown)
- Age (years), as continuous variable
- Height at baseline (cm)
- Weight at baseline (kg)
- Body mass index at baseline (kg/m^2) defined as Weight (kg)/[Height (m)]
- Women of child-bearing potential

At the time of the Double-Blind Treatment Phase database entry lock, the above information will be tabulated by treatment arm and overall using the mITT and the Double-Blind safety populations. At the time of OLE Phase database lock, the above information will be tabulated by using the OLE Safety Population.

Data will not be re-collected at entry to the OLE Phase but will be reported for the subset of patients who enter the OLE Phase.

Demographic information will be presented in a data listing. No statistical testing will be performed on the demographic data.

### **11.2.2 Medical History**

A complete medical history will be obtained at Screening to ensure patients qualify for the study and will be updated at the Baseline Visit if needed.

Medical history will be summarized by treatment arm for all patients in the safety population. Medical history data will be coded using the Medical Dictionary for Regulatory Activities (MedDRA); the version used will

---

be included in the tables and listings footnotes and summarized by system organ class and preferred term. Medical history data will be presented in a data listing.

### 11.2.3 Seizure History

Seizure history will be obtained at Screening and will be updated at the Baseline Visit if needed.

For patients in the safety population, in those patients with a history of a seizure disorder, the following aspects of their seizure history will be summarized.

- Total number of patients with a history of seizure disorder
- Whether there has been any change in seizure activity in the past 3 months (prior to the study)
- Type of seizure disorder
- Average weekly seizure frequency
- Average seizure duration in seconds

Seizure history data will be presented in a data listing.

### 11.2.4 Myotonic Dystrophy Type 1 History

Confirmation of a patient's diagnosis of DM1 will be obtained via review of the patient's medical records and genetic testing will be performed during Screening to confirm cytosine-thymine-guanine (CTG) repeat of  $\geq 100$ . Number of repeats will be summarized and listed. Age at diagnosis of DM1 will be tabulated.

Age at diagnosis of DM1 (years) = (date of diagnosis – date of birth)/365.25

The date of diagnosis of DM1 will be presented in the baseline characteristics listing.

## 11.3 Treatments

### 11.3.1 Prior, Concomitant and Prohibited Medications

Medications stopped prior to the first dose of study drug will be classified as prior medication. Medications started with or after the first dose of study drug will be classified as concomitant. Medications started before the first dose of study drug and stopped after the first dose of study drug will be classified as both prior and concomitant.

Medications will be categorized by medication group and subgroup according to World Health Organization (WHO) drug dictionary (the version used will be included in the tables and listings footnotes). Refer to the Coding Conventions document for this study.

Missing or partial medication start/stop date will be imputed as described in [Appendix 2](#). A conservative approach will be used when flagging medications.

Prior, concomitant, and prohibited medications will be summarized for the safety populations. All medications will be listed.

### 11.3.2 Prohibited and Restricted Concomitant Medications

The use of medications that may prolong the QT interval is not permitted in the study.

Use of opiates is not permitted in the study.

Use of strong cytochrome P450 (CYP) 2D6 inhibitors or strong CYP3A4 inducers is not permitted during the Double-Blind Treatment Phase of the study, and if being used, should be discontinued at Screening; washout of 5 half-lives of these medications is required prior to enrollment and initiating study drug. These medications (examples are listed in [Appendix 3](#)) are allowed during the OLE Phase of the study, but adjustments to the dose of pitolisant is required.

---

Pitolisant increases the levels of histamine in the brain; therefore, centrally acting H1R (histamine 1 receptor) antagonists (sedating antihistamines) that cross the blood-brain barrier may reduce the effectiveness of pitolisant. Concomitant use of centrally acting or sedating H1R antagonists is not permitted during the Double-Blind Treatment Phase of the study (requires a washout of 5 half-lives prior to randomization). Although not prohibited during the OLE Phase of the study, use of these medications should be avoided and, if needed, will require consultation with the Medical Monitor.

Prohibited medications taken in the study will be reported and summarized with the protocol deviations.

Prior and concomitant medications will be summarized based on the number and percentage of patients using each medication along with the number and percentage of patients using at least one medication within each medication group and subgroup.

For patients who opt to continue in the OLE Phase of the study, only medications started on or before the last dose in the Double-Blind Treatment Phase will be included in the summaries for the Double-Blind Treatment Phase. Medications started after the last dose and up to 30 days after the last dose of treatment in the Double-Blind Treatment Phase will be included in a separate listing in the Double-Blind Treatment Phase and also summarized in the OLE Phase.

